- **Medical History Questionnaire:** Subjects may refrain from answering questions if they do not wish to do so. There are no risks from completing the questionnaire.
- **Anthropometric Measurements and Vital Signs.** The PBRC outpatient and inpatient clinic staff are trained to perform these procedures in accordance with PBRC standards of practice. There are no risks involved.
- **Urine Test.** The staff of the phlebotomy unit collect the urine in accordance with standard operating practices. There are no risks involved.

In addition to the risks listed above, participants may experience a previously unknown risk or side effect.

Minimizing risks

Continuous monitoring by the Co-PI and/or the medical investigator of the study will minimize all potential risks and discomforts. Research participants will be immediately withdrawn from the study if participation in the study becomes an unreasonable risk to the subject.

Potential Benefits to Subjects

Based on the preliminary data, there is high likelihood that subjects may have improvements in the biochemical measures evaluated in the study. Subjects will gain knowledge of effective diet prescriptions for improvements in metabolic health. Since the changes are small, it is expected that subjects will be able to sustain these lifestyle changes over the long term.

PAYMENT FOR PARTICIPATION

At the completion of all study visits and procedures, participants will be paid \$200 for the time spent in the clinic. Subjects will receive \$75 for the Baseline visit and \$125 for Visit 9. This compensation is in line with all the other studies conducted at the Pennington Biomedical Research Center.

EMERGENCY CARE AND COMPENSATION FOR RESEARCH-RELATED INJURY

No form of compensation for medical treatment is available from the Pennington Biomedical Research Center. In the event of injury or medical illness resulting from the research procedures the research volunteer (from any group) will be referred to their physician/surgeon or a treatment facility. The Pennington Biomedical Research Center is a research facility and provides medical treatment only as part of research protocols. Should a volunteer require medical treatments, community physicians and hospitals must provide them to him/her.

SHARING OF RESULTS WITH SUBJECTS

The screening lab results will be shared with the subjects on their first testing visit. At the end of the study, a manuscript will be prepared for submission to a peer-reviewed journal. A summary of the results will be posted on ClinicalTrials.gov which subjects may access.

RESOURCES AVAILABLE

The Outpatient and Inpatient research units and the Metabolic Kitchen are well equipped and staffed to carry out the requirements of this study and appropriate standards of practice are in place to ensure appropriate research procedures.

ECONOMIC BURDEN TO SUBJECTS

There are no costs for which the subjects will be responsible.

CONSENT PROCESS

Written informed consent will be obtained in the outpatient research clinic by the coordinators and one of the physicians will be available to answer questions if needed. A waiting period will be allowed, if desired by the participant. The coordinators and investigators will be available for questions throughout the study.

SIGNIFICANCE OF THE STUDY

Insulin resistance is a hallmark of obesity and lies along the continuum of type 2 diabetes which remarkably affects 9.4% of the US population.² The debilitating complications of diabetes include heart disease, stroke, amputations, end-stage renal disease, and blindness. Thus, research that focuses on preventing diabetes, and finding a treatment that is cost efficient is important. Potatoes are recognized as a starch-rich vegetable and denigrated for their role in contributing to obesity and diabetes, regardless of how they are prepared. However, potatoes

are a low-cost source of critical nutrients, high-quality protein, and phytochemicals which are largely ignored. Given their frequency of consumption, potatoes are clearly available, familiar, and taste good, which gives them an unassailable edge over other plant foods as a means of cutting the meat in a dish. Our randomized controlled feeding study will be the first trial to test this deceptively simple strategy to enhance the overall quality of the diet and provide health benefits. More importantly, these small changes are likely to be sustained over time. Further, we expect that the potato will hold its own in a fair comparison with pulses, a food that is frequently promoted for its health benefits.

APPENDIX 1

[figure not shown]
Table 1. Volume of blood drawn at Screening, Baseline, and Visit 9

Test	Screening	Baseline	Visit 9
	Blood (ml)	Blood (ml)	Blood (ml)
CBC	4		4
Chemistry 15/Insulin	4		4
Lipids		4.5	
LDL particle size		1.5	1.5
Glucose and Insulin (MTT)		15	12.5
Total	8	21	22

Notes: (1) Chemistry 15 includes fasting glucose and lipids (2) IV blood draw volumes include 0.5 ml returned during blood draw.

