The objective of the present application is to develop a diet intervention to reverse insulin resistance in an overweight or obese population. For US adults, the white potato ranks among the top 15 foods providing key nutrients such as potassium and dietary fiber.²³ Pulses are a highly recommended food that contribute as much dietary fiber to the diet of US adults as potatoes.⁵³ Our central hypothesis is that in the context of an overall healthy eating pattern, potatoes and pulses will not differ in the glycemic and insulinemic responses, lipid profile, and hsCRP concentration they elicit. The rationale for the proposed study is that by developing a small changes sustainable approach to reducing meat intake and reducing the glycemic load of the diet, we can slow and ultimately prevent the progression to diabetes in individuals with untreated insulin resistance. We plan to test our hypothesis and accomplish the objective of this application by pursuing the following specific aims:

Aim 1. Compare the effect of diets containing white potato/lean meat (PLM) and pulses/lean meat (LMP) main entrées for eight weeks on the glycemic response in 36 overweight or obese, insulin resistant adults. This aim requires a randomized controlled feeding trial of potato and lean meat in the ratio 40:60 + starchy staple (potato), and pulses and lean meat (40:60) + starchy staple (bread, rice, pasta). The primary outcome is the glycemic response to the diets.

Hypothesis. The mean glycemic response will improve compared to baseline in the PLM and LMP groups but the two diets will be non-inferior to each other.

Aim 2. Evaluate changes in insulin, total cholesterol, high density lipoprotein cholesterol (HDL) low density lipoprotein cholesterol (LDL), triglycerides, LDL particle size, and high sensitivity C-reactive protein (hsCRP) in response to eating the PLM or LMP diets for eight weeks.

Hypothesis. Blood lipid, insulin, and hsCRP levels will improve, and the LDL particle size will increase compared to baseline in the PLM and LMP groups, but the two diets will not differ from each other.

RESEARCH DESIGN AND METHODS

The experimental plan is presented in Figure 1.

[figure not shown]

Figure 1. Study Schema

*Homeostatic model assessment of insulin resistance

Study Subjects

This study will enroll 36 overweight or obese male and female subjects. Subjects will be enrolled on the basis of the following eligibility criteria:

Inclusion Criteria

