Subjects will arrive at the clinic in the morning following an overnight fast (except for water) that began no later than 8 hours prior to the study appointment. The following procedures and measurements will be performed:

- Measurement of metabolic weight and vital signs (blood pressure, pulse, and temperature).
- Blood collection for measurement of CBC, Chemistry 15 panel, LDL particle size, and hsCRP.
- Three-hour MTT with glucose and insulin.
- Recording of VAS ratings of satiety measures
- Recording of adverse events.

STUDY PROCEDURES

Diets. The main entrée in the PLM and LMP arms will consist of a menu item in which 40% of the meat in the original recipe will be replaced with potatoes or pulses, respectively. The diets are designed to provide six ounces or less of meat/day which is consistent with the US dietary guidelines as well as the DASH diet, and constitutes approximately half the average daily meat intake in the US. Potatoes used in the meal preparation will be unpeeled, pre-cooked, refrigerated for 12 - 24 hours, and reheated or served cold.

These partially substituted meat dishes will constitute the main entrée at lunch and dinner and each dish will be accompanied by a starchy staple consisting of potato (PLM diet) and bread,

rice, or pasta (LMP diet). Additionally, the PLM and LMP diets, matched for their carbohydrate and dietary fiber content will consist of whole grains, fruits, vegetables (excluding additional potatoes and pulses), dairy products, seafood, nuts, and seeds as part of a healthy eating pattern. The diets will meet the Institute of Medicine Dietary Reference Intakes recommendations of the acceptable macronutrient distribution range for adults.⁵⁴ Caloric needs for weight maintenance will be determined using the Mifflin St. Jeor formula for estimation of basal metabolic rate⁵⁵⁻⁵⁷ and multiplied by an activity factor based on subjects' activity level. All foods will be provided to the subjects during the eight week study period. Subjects will report to the PBRC each week to collect the foods according to their diet plan. The meals will comprise foods that have been prepared in advance and frozen, dry packaged foods, and frozen foods. Subjects will be instructed to return all containers and any uneaten food items. The Metabolic Kitchen staff will meet with the subject and evaluate compliance.

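### The central hypothesis and significance wording claim a result for potatoes versus pulses, but the trial compares two complete diets that also differ in their starchy staple

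*Combined protocol and SAP*

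**What the plan says.** **What each arm eats.** Aim 1 defines PLM as "potato and lean meat in the ratio 40:60 + starchy staple (potato") and LMP as "pulses and lean meat (40:60) + starchy staple (bread, rice, pasta"). The Diets section under Study Procedures confirms that at lunch and dinner "each dish will be accompanied by a starchy staple consisting of potato (PLM diet) and bread", rice or pasta in the LMP diet. It also says the two diets are "matched for their carbohydrate and dietary fiber content", and that the vegetables in the rest of the diet add no further potatoes or pulses.

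**Where the claim is at diet level.** The abstract's hypothesis, the hypotheses under Aims 1 and 2, the primary outcome in Aim 1, and Power and Sample Size all speak of the PLM and LMP diets or groups.

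**Where the claim is at food level.** Four places speak of the foods:
- Hypothesis and Specific Aims, central hypothesis: "Our central hypothesis is that in the context of an overall healthy eating pattern, potatoes and pulses will not differ" in their effects on glucose, insulin, lipids and hsCRP.
- The end of Preliminary Data, which argues from the similarity of the two foods to their non-inferiority.
- The expected result that closes the abstract's study design, which predicts improvement with potatoes and pulses and non-inferiority between them.
- Significance of the Study: "we expect that the potato will hold its own in a fair comparison with pulses".

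No section explains why the staple differs between arms, and none limits the conclusion to the complete diets.

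**The concern.** Two components change together between the arms: what replaces 40% of the meat in the entrée, and which starch is served beside it. The second is a large carbohydrate source at two meals a day for eight weeks, and the primary outcome is a glucose response. A reader of the central hypothesis would take a positive result to mean that potatoes perform as well as pulses. The trial would have shown something narrower: that a diet with potato in both roles performs like a diet with pulses in one role and a grain staple in the other.

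This matters more when the aim is to show similarity. In an equivalence or non-inferiority comparison, two effects of opposite sign offset each other and the result looks like success. The reverse can also happen: a staple effect alone can make the diets differ when the entrées do not. In either case a food-level conclusion would be wrong even though the test was run correctly.

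**Working it through.** **1. What the contrast contains.** Write M(entrée, staple) for the mean glucose response. The trial observes two cells, M(potato, potato) in PLM and M(pulse, grain) in LMP. Their difference splits exactly as

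PLM − LMP = [M(potato, potato) − M(pulse, potato)] + [M(pulse, potato) − M(pulse, grain)] = p + s,

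where p is the entrée effect with the staple held at potato, and s is the staple effect with the entrée held at pulse. No additivity is assumed. The middle cell, M(pulse, potato), is never observed; nor is M(potato, grain), which gives the alternative split. The data therefore determine p + s and nothing about p or s separately. More subjects, covariates or a different covariance structure cannot change that, because staple and arm are the same variable.

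**2. What the matching achieves.** Equal carbohydrate and fiber removes differences in p and s that arise from the amounts of those nutrients. It does not equalize starch type or preparation. Potatoes and Food Applications itself treats cooling, resistant starch and added fat as influences on the glucose response. The Diets section has potatoes cooked ahead and chilled for 12 to 24 hours, and describes no comparable step for bread, rice or pasta.

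**3. The plan's own figure.** Power and Sample Size gives 80% power with 15 per group and a margin of 40 mmol × min/L. Alpha, sidedness and the standard deviation used (12.5 or 28.2) are not stated. For two one-sided tests with a true difference of 0, n = 2 × [SD × (z(1−α) + z(0.90)) / 40]². Assuming α = 0.05 for each test:
- SD 28.2: 2 × (28.2 × 2.926 / 40)² = 8.5, so 9 per group.
- SD 12.5: 2 × (12.5 × 2.926 / 40)² = 1.7, so 2 per group.

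The 15 is not reproduced from these inputs. That is a separate matter, and nothing here depends on it.

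**4. A purely algebraic illustration.** The chance of declaring equivalence depends on p and s only through their sum. The values below are chosen to show this and are not estimates; the documents give neither p nor s. Inputs: 15 per group, margin 40, α = 0.05 per one-sided test (assumed), t-based power. The second SD column assumes that 12.5 is a standard error from 11 subjects: 12.5 × √11 = 41.5.

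| p | s | p + s | SD 28.2 | SD 41.5 |
|---|---|---|---|---|
| 0 | 0 | 0 | 97% | 65% |
| +60 | −60 | 0 | 97% | 65% |
| +60 | −40 | +20 | 60% | 35% |
| 0 | +40 | +40 | 5% | 5% |

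Row 2 has an entrée effect of 60/40 = 1.5 times the margin and cannot be told apart from row 1. Row 4 has no entrée effect, and equivalence is almost always missed. The first is masking and the second is a created difference.

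**The case against.** The strongest reply is that the trial tests what it says it tests. The aim hypotheses, the primary outcome and the power statement all concern the PLM and LMP diets, Aim 1 spells out both staples, and Statistical Analysis prespecifies no food-level conclusion. This stands, and it limits the point. A reader might infer that Aim 1 is invalid or the comparison unusable. The documents do not support that: comparing two whole diets is legitimate, and randomization supports it.

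Three of the four food-level statements also carry a qualifier that places the foods within a healthy eating pattern. This softens them, but such a qualifier suggests a shared background, and here part of the background differs by arm. The significance statement has no qualifier.

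The matching on carbohydrate and fiber, the exclusion of further potatoes and pulses, and the inclusion of whole grains in both arms all limit how far the diets diverge. This stands as mitigation. It does not separate the two effects.

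A reader might also infer that the design hides a disadvantage of potato. Preliminary Data does say that the evidence for pulses is much stronger, and the chilled potato staple could offset such a disadvantage. But the documents report neither effect. An entrée effect of 60 would be 60/96 = 62.5% of the whole mixed-meal incremental area quoted from the source study, so the illustration should not be read as likely. The opposite error is equally possible.

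Finally, the Meal Tolerance Test section does not give the composition of the test meal, so it is unclear whether the staple is eaten during the test. If it is not, the acute part of the glucose contrast is less affected. The Visit 9 response and the fasting secondary outcomes would still follow eight weeks on diets that differ in staple.

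**Conclusion.** The point holds as a mismatch between what the trial estimates and what four statements claim. The PLM-versus-LMP contrast is sound at the level of complete diets. The central hypothesis, the rationale at the end of Preliminary Data, the abstract's expected result and the significance section go beyond it by speaking of potatoes and pulses as foods. The confounding of staple with arm is complete, and carbohydrate and fiber matching narrows it without removing it.

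The size and direction of any resulting error cannot be stated, because the documents contain no figure for the staple effect. The conclusion rests only on the arm definitions and on the absence of any arm or design element that holds the staple constant. It does not rest on the illustrative values, the assumed alpha or the sample-size calculation.

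**What to change.** Change wording in four places, and carry the same wording into the conclusion of any report:

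- In the central hypothesis, the closing sentence of Preliminary Data, the abstract's expected result and Significance of the Study, replace potatoes versus pulses with the two complete eating patterns: potato/meat entrée with potato staple, and pulse/meat entrée with bread, rice or pasta. State the claim as equivalence or non-inferiority of those patterns, whichever the plan adopts.
- Add one sentence saying that a result, in either direction, cannot be attributed to potato versus pulses alone because the staple also differs.
- Remove the description of the trial in Significance of the Study as a fair comparison with pulses.

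The Aim 1 and Aim 2 hypotheses, the primary outcome and the power statement need no restatement on this account. Diets, visits, sample size and model are unchanged. The cost is a narrower claim: the trial could no longer be presented as evidence about the two foods themselves.

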Recruitment. Subjects will be recruited through the use of printed material, targeted solicitation through the Pennington Biomedical Research Center (PBRC) email listserv and social media. Participants will complete an online screening and will be contacted by a PBRC recruiter for a brief telephone interview to assess eligibility criteria, prior to being scheduled for a clinic visit. Subject eligibility criteria will be evaluated at a single screening visit. The screening visit will occur in the outpatient clinic, in the morning following confirmation of an overnight (at least 8 hours) fast. Subjects who provide informed consent will proceed with the tests and measurements of the screening visit. Subjects who satisfy the eligibility criteria will be enrolled in the study. The schedule of assessments is provided in Table 1.

Randomization and Blinding. Subjects will be randomly assigned to one of two groups (n = 18 per group). [name], the biostatistician from the PBRC Biostatistics group will be responsible for the randomization design, assignment of treatment groups, and statistical analyses plans including power and sample size. Except for the Director of the Metabolic Kitchen and the dietitian assigned to the study, all other researchers conducting the study will be blinded to the treatment group assignment of subjects.

CLINIC VISITS

Subjects will complete one screening visit and nine study visits.

Table 1. Schedule of Assessments

Procedure	Screening	Baseline	Visits 2 - 8	Visit 9
Infomed Consent	x			
Height/Waist Circumference	x			
Weight	x	x	x	x
Vital Signs	x	x		x
Chemistry 15 Panel/CBC	x			x
Insulin	x			
Urine Pregnancy Test**	x			
Lipids/LDL Particle Size/hsCRP		x		x
Medical History Questionnaire	x			
Adverse Events		x	x	x
Medications	x			
Meal Tolerance Test		x		x
Visual Analog Scales (Satiety)	x			x
Study Foods Dispensing		x	x	
Compliance			x	x
Nutrition Counseling		x	x	

*Women of child-bearing potential

Screening Visit (1½ hours)

Subjects will report to Pennington Biomedical in the morning following an overnight fast (except for water) that began no later than 8 hours prior to the study appointment. The screening visit includes explanation of the study purpose, procedures, and signing of the informed consent. If the participant agrees to participate by signing a consent form, the following procedures will be performed:

- Self-report of personal and family medical history.

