Power and Sample Size. Power for this study is based on a parallel arm design with the potato/lean meat diet (PLM) and pulses/lean meat diet (LMP) groups. Equivalence in blood glucose will be the primary outcome. A similar crossover study by Hatonen *et al.*,⁴³ using 11 subjects, showed that adding meat, fat, and vegetables to a potato meal reduces the incremental area under the curve for glucose (iAUC) in a MTT. The iAUC was lower after the mixed meal ($96 \pm 12.5 \text{ mmol} \times \text{min/L}$) than after potato alone ($197 \pm 28.2 \text{ mmol} \times \text{min/L}$). Long interventions using crossover designs with washout periods are associated with high dropout rates.⁵⁸ In our experience, recruitment rates are slow and drop-out rates are high, especially, when there is no symptomatic improvement that is obvious to subjects participating in the trial. Therefore, we will use an eight-week parallel arm design.

We assume the standard deviation estimates from the study by Hatonen *et al.* to be similar to this proposed study since the PLM and LMP daily diets will also reduce the meat content in an overall healthy eating pattern which has been shown to lower the glycemic or insulinemic responses.^{50,59,60} Further, our trial is a controlled feeding study in which all meals are provided and compliance is tightly monitored by registered dietitians. This study has 80% power to show equivalence between the two groups with at least 15 subjects per group given that the difference between the two groups is no larger than 40 mmol \times min/L. Allowing for approximately 20% loss to follow-up, or 3 subjects per group, this study will enroll a total of 36 subjects.

Statistical Analysis. The secondary outcomes are changes in insulin, lipid concentrations, LDL particle size, and hsCRP. Mixed effect linear models will all be used to estimate changes across the eight weeks for primary and secondary outcomes. Normality of model residuals will be checked and transformation will be applied where necessary. An unstructured covariance matrix will model the within-subject effects. Missing data is assessed using a sensitivity analyses which will use several different sets of models under different assumptions. Covariates, like age, race, and gender will be determined using Akaike information criterion (AIC) as the model fit criteria.

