We will attempt to retain program participants once randomized for study completion through the end of study visit. It is our desire to analyze results on all participants who were enrolled in the study. In accordance with the declaration of Helsinki/Tokyo/Venice/Hong Kong, participants have the right to withdraw from the program at any time for any reason. The investigator also has the right to withdraw participants from the program treatments in the event of inter-current illness, adverse experience, treatment failure, protocol violation, or other reasons. Should a participant decide to withdraw from treatment, all efforts will be made to complete and report follow-up observations as thoroughly as possible.

RISKS/BENEFITS

The study involves the following risks:

- **IV Procedures/Blood Draws:** There is the possibility of discomfort, pain, and bruising at the vein on the arm where the needle is inserted. There may also be a small risk of bleeding and a very small risk of infection at the site of the blood draw. Sterile technique and trained personnel minimize these risks.
- **Study Foods.** The meals provided during the study are foods that are ordinarily consumed by people and are cooked and stored using methods common in food preparation. The research dietitians and staff of the research kitchen are experienced in developing, preparing, storing, and dispensing study-specific food products developed to meet the needs of the study. Additionally, subjects will be asked to inform staff about any food allergies or intolerances. A dietary questionnaire is routinely administered at the screening visit when the study involves a meal service. Research dietitians are responsible for managing the dietary component of specific study protocols. A continuous quality assurance program is followed to check food item weights, recipe procedures, packaging of meals, and food temperatures. Documentation is maintained for each study. All Metabolic Kitchen staff members receive training in food sanitation and in research diet preparation. Therefore, there is no risk associated with the meals provided by the Pennington Metabolic kitchen.
- **Nutrition Counseling.** There is minimal risk associated with behavioral counseling. Sessions are confidential and the counselor is trained to minimize any discomfort that is associated with the discussions during the sessions.

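### Does the loss allowance of about 20%, or 3 subjects per group, misstate what an enrolment of 36 can absorb?

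*Combined protocol and SAP*

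**What the plan says.** The Power and Sample Size paragraph under Statistical Considerations sets the minimum number of completers: "This study has 80% power to show equivalence between the two groups with at least 15 subjects per group". It then moves from completers to enrolment: "Allowing for approximately 20% loss to follow-up, or 3 subjects per group, this study will enroll a total of 36 subjects". The Randomization and Blinding paragraph gives the same allocation, 18 in each of two groups, and the abstract and Aim 1 also give 36.

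On subjects who leave, the Withdrawal of Subjects section says that after withdrawal from treatment "all efforts will be made to complete and report follow-up observations as thoroughly as possible". The Statistical Analysis paragraph adds: "Missing data is assessed using a sensitivity analyses which will use several different sets of models under different assumptions".

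The plan does not say whether the percentage is taken of the required completers or of those enrolled.

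**The concern.** Loss to follow-up happens among people who have been enrolled, so most readers would take a loss percentage to be a share of enrolment. On that reading the two halves of the sentence disagree: 3 of 18 is 16.7%, not 20%. The 20% appears only when the 3 is divided by the 15 completers. This looks like a common slip, multiplying the required number by one plus the loss rate where one should divide by one minus the loss rate.

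The discrepancy runs in the uncomfortable direction. Someone who takes away only the percentage would think that the trial can lose a fifth of its subjects and still keep 15 per group, when the enrolment target covers one sixth. The same paragraph also remarks: "In our experience, recruitment rates are slow and drop-out rates are high". If the allowance were too thin, the primary equivalence comparison could finish below the size that the plan ties to 80% power.

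**Working it through.** **Inputs from the documents.** Power and Sample Size: at least 15 completers per group, a stated loss of about 20%, 3 losses per group, 36 enrolled, 80% power, a margin of 40 mmol x min/L, and printed spreads of 12.5 (mixed meal) and 28.2 (potato alone) from the cited 11-subject crossover study. Randomization and Blinding: 18 per group.

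**Reproducing the plan's total.**
- By counts: 15 + 3 = 18 per group; 2 x 18 = 36. This agrees exactly.
- By the percentage applied to completers: 15 x 1.20 = 18 per group, 36 in total. This agrees exactly.

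**The two possible bases.**
- Of the required completers: 3/15 = 20.0%.
- Of those enrolled: 3/18 = 6/36 = 16.7%.
- Difference: 20.0 - 16.7 = 3.3 percentage points.

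**If 20% of those enrolled was meant.**
- Completers left from 18: 18 x 0.80 = 14.4 per group, which is 15 - 14.4 = 0.6 short on average.
- Enrolment that covers it: 15 / (1 - 0.20) = 18.75, so 19 per group and 38 in total, 2 more than planned.
- Enrolment that covers a loss of one sixth: 15 / (1 - 1/6) = 18 per group, 36 in total.

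**What the shortfall could cost in power.** The whole-number outcome nearest to a 20% loss of 36 is 7 losses (7/36 = 19.4%). That leaves 29 completers, for example 14 and 15. Power was computed for two one-sided t-tests with margin 40. The plan gives no alpha and no assumed true difference, so two one-sided levels are shown and the true difference is taken as 0.

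| Standard deviation | One-sided alpha | Power, 15 and 15 | Power, 14 and 15 |
|---|---|---|---|
| 12.5 (printed, read as an SD) | 0.05 or 0.025 | above 99% | above 99% |
| 28.2 (printed, read as an SD) | 0.05 | 96.8% | 96.2% |
| 28.2 (printed, read as an SD) | 0.025 | 92.6% | 91.4% |
| 36.5 (solved so that 15 and 15 gives 80%) | 0.05 | 80.0% | 78.1% |
| 32.6 (solved so that 15 and 15 gives 80%) | 0.025 | 80.0% | 77.8% |

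The last two standard deviations appear nowhere in the documents. They were chosen so that 15 per group gives exactly the stated 80%. Under them, one completer fewer costs 80.0 - 78.1 = 1.9 or 80.0 - 77.8 = 2.2 points. The table takes the 15 as given. It does not test whether 15 per group is adequate, which depends on the standard deviation and is a separate question.

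**The case for a change.** The strongest case for acting is that the repair costs one phrase and that 20% is not a loose rounding of 16.7%: it is exactly 3/15, the pattern left by inflating the wrong way. A percentage can also be carried into reports or retention targets without the count beside it. Neither follow-up after withdrawal nor a mixed model recovers the Visit 9 outcome of a subject who is truly lost.

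Part of this stands. The arithmetic is right, the base is not stated, and enrolled subjects are the more natural base. If the investigators really expected to lose 20% of those enrolled, 18 per group is one short of the usual inflation.

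The rest is weaker. The base of 15 comes from the sentence just before, and 20% of it is exactly 3, so the percentage is correct on a base that the paragraph itself supplies. The count is printed beside it, so a reader of the sentence knows how many losses are covered. The remark on high drop-out follows a sentence about crossover designs with washout and leads to the choice of a parallel design; it does not comment on the size of the allowance. Nor do the documents show that relabelling to about 17% is the right correction. That is one of two ways to reconcile the sentence (the other is to enrol 38), and nothing says which was intended.

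**Conclusion.** No change to the plan is needed. This is an unstated denominator, a clerical matter, and not a wrong sample size. The figures that govern conduct (15 completers, 3 losses, 18 per group, 36 in total) agree with one another wherever they appear. Rewording the percentage would alter no enrolment number, analysis or conclusion.

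If the percentage refers to required completers, nothing is off. If it refers to those enrolled, it is 3.3 points too high, and the average shortfall at a true 20% loss is 0.6 of a subject per group. The largest power cost calculated for 14 and 15 completers is about 2 points, and only with a standard deviation chosen so that 15 per group gives exactly 80%. With either printed spread read as a standard deviation, power with 14 and 15 stays at 91% or more. These power figures assume a true difference of 0 and a one-sided alpha of 0.05 or 0.025, neither of which the plan states, and they are no evidence that 15 per group is itself enough.

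Anyone quoting the allowance can add the base: 20% of the 15 required, about 17% of the 18 enrolled.
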